## Statistical analysis

### 1) Course of illness leading to reoperative anti-reflux surgery

Data will be analyzed using STATA15. Descriptive analysis of age, sex, comorbidity (Charlson Comorbidity Index, ASA-score, BMI, alcohol/tobacco use), complications to surgery, rate of endoscopic dilation and mortality comparing patients with only primary anti-reflux surgery and patients with reoperation during the study period, will be performed using Student's t-test, Chi2-test and Mann-Whitney-U test.

Logistic regression will be performed with reoperation (laparoscopic, open or other) as primary outcome and age, sex, comorbidity (Charlson Comorbidity Index, ASA-score, BMI, alcohol/tobacco use), complications to surgery and endoscopic or surgical procedure during study period as independent variables. If the number of patients is sufficient, subanalysis will be performed with emergency reoperation as dependent variable/outcome.

Secondary analysis will be performed using Cox-regression investigating time to reoperation with age, sex, comorbidity (Charlson Comorbidity Index, ASA-score, BMI, alcohol/tobacco use), complications to surgery and endoscopic or surgical procedure during study period as independent variables.

*2) Utilization of treatment of gastroesophageal reflux disease.*

The rate of anti-reflux surgery per 100.000 inhabitants for each year during the study period will be calculated using census data from Statistics Denmark. From MEDSAT the rate of use of pharmacological anti-reflux treatment per 100.000 inhabitants will be calculated using abovementioned census-data. Trends in the utilization of surgery are investigated with trend-analysis in the form of Poisson-regression alternatively negative binominal regression.

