## Aim

The purpose of this study is to investigate course of illness leading to reoperation after primary anti-reflux surgery and investigate the utilization of anti-reflux treatment, both medical and surgical, in the period 2000-2017

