Despite the high success rate of anti-reflux surgery, reoperation does occur. The indication for reoperation is most often recurrence of reflux symptoms or dysphagia, and reoperation should be preceded by thorough investigation and possible endoscopic balloon-dilation (15). Laparoscopic reoperation is both feasible and safe, but has been linked to higher morbidity, higher risk of conversion to open surgery and longer length of stay. The final result seem to result in less patient satisfaction than primary surgery, but the available evidence is limited by a high risk of bias due to small sample size and a possible underreporting of complications (16, 17).

An American study reported a cumulative five- and ten year incidence of reoperation of 5.2% and 6.9% respectively. The rate of reoperation was highest in the first year after primary anti-reflux surgery. 30% of reoperations were performed in a different center than the primary procedure. In a Danish study, Funch-Jensen et al (18), investigated rate of reoperation in Denmark 1997-2005 and calculated a rate of 5% without significant differences in length of stay, rate of complications or mortality compared to primary

surgery. Reoperation was however associated with a higher rate of conversion to open surgery with a tendency towards higher rates of conversion in low-volume centers. As in the American study, reoperation was often performed at different centers than the primary procedure. Whether this was the result of centralization or patient's wishes is unknown.

It is our hypothesis, that from 2000-2017, reoperative anti-reflux surgery was performed primarily with a laparoscopic approach without increased length of stay or rate of complications compared to primary surgery. Due to increased surgical experience the rate of complications is decreasing despite increased comorbidity. Endoscopic balloon-dilatation delays reoperation but does not prevent it.

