## Methods

The study is a two-part register-based cohort study based on data from The National Patient Registry, The Civic Registry and Danish Anaesthesia Database in the period 1996-2017. The two individual parts of the study concerns the same population.

The population is defined as all adult Danish patients undergoing anti-reflux surgery (Nomesco: KJBC00, KJBC01, KJBC02, KJBW96, KJBW97) from 2000-2017 identified from The National Patient Register.

Age, sex, Charlson Comorbidity Index at date of surgery and length of stay in relation to any surgery and any surgical or endoscopic procedure performed after anti-reflux surgery (including diagnosis 30 days postoperatively to establish possible morbidity) are derived from the National Patient Registry.

ASA-score, weight, height, use of alcohol or tobacco and priority of any surgery (emergency or planned) during the study period are retrieved from The Danish Anaesthesia Database. From the Civic Register, data on mortality in the study period are retrieved.

Information on the use of pharmacological treatment for gastroesophageal reflux disease on population level is retrieved from MEDSTAT and data on population size on population level are retrieved from Statistics Denmark.

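### The hypothesis that redo surgery has no longer stay and no more complications than primary surgery is left untested: length of stay is never analysed, and complications are compared only by whether a patient was later reoperated

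*Combined protocol and SAP*

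**What the plan says.** The last paragraph of the Background hypothesises that reoperative surgery in 2000-2017 was done "without increased length of stay or rate of complications compared to primary surgery". This is a statement about operations: redo against primary.

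Methods plans to retrieve "length of stay in relation to any surgery" from the National Patient Registry. It also plans to retrieve "any surgical or endoscopic procedure performed after anti-reflux surgery (including diagnosis 30 days postoperatively to establish possible morbidity".

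Statistical analysis, part 1, has three components:

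- A descriptive comparison that includes "complications to surgery, rate of endoscopic dilation and mortality comparing patients with only primary anti-reflux surgery and patients with reoperation during the study period".
- A logistic regression with reoperation as the primary outcome.
- A secondary Cox regression of time to reoperation.

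Both regressions take "complications to surgery and endoscopic or surgical procedure during study period as independent variables". Length of stay is named in none of the three, nor in part 2. No section says whether complications are those after the primary operation, after the reoperation, or after either.

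**The concern.** The hypothesis compares two kinds of operation. The planned table compares two kinds of patient, those never reoperated and those eventually reoperated. No analysis has complications or length of stay as the outcome and type of operation as the exposure.

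The question matters to this study. The Background reports that reviews link redo surgery to higher morbidity and longer stay, that an earlier Danish national study found no significant difference, and that the available evidence is limited by small samples and possible underreporting. A national register is well placed to add to this. Followed as written, the plan would give no result on length of stay and probably none on redo complications. There is also a risk of misreading: the complications row in the patient table could be taken as the answer to the hypothesis.

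**Working it through.** **Length of stay.** The documents give no figure to reproduce, so this is a check of the text. Length of stay is in the hypothesis (Background) and in the data to be retrieved (Methods). It is absent from the descriptive list, the logistic model, the Cox model and part 2. No assumption is needed.

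**Complications: what each reading would show.** The documents give no complication rates, so these are assumed.

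- p = complication risk at a primary operation: 3, 5 or 10% (assumed).
- f = proportion reoperated: 5% (the earlier Danish rate) or 6.9% (the ten-year American figure), both from the Background.
- k = relative risk of reoperation after a complicated primary: 1, 2 or 3 (assumed).
- q = reoperation risk after an uncomplicated primary = f / ((1 - p) + k p).

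*Reading 1: complications of the primary operation.* This is the likeliest reading, because the same term is used to predict reoperation.

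- Rate in reoperated patients = p k q / f.
- Rate in never-reoperated patients = p (1 - k q) / (1 - f).
- Example with p = 5%, k = 2, f = 5%: q = 0.05 / 1.05 = 0.0476. The rates are 9.52% and 4.76%, ratio 2.00.
- Example with p = 5%, k = 3, f = 6.9%: q = 0.069 / 1.10 = 0.0627. The rates are 13.64% and 4.36%, ratio 3.13.
- Over all combinations the ratio is 1.00 for k = 1, 1.90-2.09 for k = 2 and 2.71-3.27 for k = 3.

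The complication rate of redo surgery appears in neither formula. The row would read the same whether redo surgery had half, the same or three times the primary rate.

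*Reading 2: redo operations against the primaries of never-reoperated patients.* With no true difference the ratio is p divided by the never-reoperated rate. It is 1.00 for k = 1 and 1.045-1.157 for k = 2 to 3. The comparison is only partial, because the primaries of later-reoperated patients drop out.

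*Reading 3: all of a patient's operations.* This is the least natural reading. With equal, independent risk at each operation, the ratio is (1 - (1 - p)²) / p:

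| p | two operations | ratio |
|---|---|---|
| 3% | 5.91% | 1.97 |
| 5% | 9.75% | 1.95 |
| 10% | 19.0% | 1.90 |

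**Precision of a direct comparison.** Half-width of the 95% interval for a difference in proportions = 1.96 √(p(1 - p)(1/n1 + 1/n0)). The numbers of operations are assumed, with redos at 5% of primaries.

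| p | 100 redos, 2,000 primaries | 300 redos, 6,000 primaries |
|---|---|---|
| 3% | 3.4 points | 2.0 points |
| 5% | 4.4 points | 2.5 points |
| 10% | 6.0 points | 3.5 points |

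**The case against.** The strongest reply is that the Aim is "The purpose of this study is to investigate course of illness leading to reoperation after primary anti-reflux surgery", together with utilisation of treatment. For that aim a patient-level table and models of reoperation are the right tools, and complications of the primary operation are a proper candidate predictor. This stands. The redo-versus-primary contrast appears only as a hypothesis closing the Background. It is nonetheless stated explicitly, and length of stay has no role in part 1 as written.

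A second reply is that adjustment goes beyond the crude contrast in the hypothesis, and that an interval alone does not establish that there is no increase. Both parts are fair. Crude estimates should therefore be given beside adjusted ones, and the conclusion may have to be modest.

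Three stronger readings are tempting, and the documents do not support them.

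- *The planned complications comparison is biased two- to threefold.* On the likeliest reading, a ratio of 1.9-3.3 would be a valid association between a complicated primary and later reoperation. Near-doubling with no true difference arises only if all operations are counted.
- *The mortality comparison is biased.* Patients must survive to be reoperated, so a crude comparison of long-term death would favour the reoperated group. But the plan says only mortality. The study period in Methods is a retrieval window, and perioperative death is possible. The point is conditional.
- *Redo operations misclassified as primary would spoil the comparison.* The population is taken "from 2000-2017 identified from The National Patient Register", while data sources including the "Danish Anaesthesia Database in the period 1996-2017" reach further back, so look-back is available. If a share c of operations classed as primary were really redos, a true ratio of 2.00 would read 2 / (1 + c). For an assumed c of 0.1-4.0% that is 2.00 to 1.92.

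**Conclusion.** The point holds as an untested hypothesis, not as a wrong estimate. For length of stay the gap is plain from the text. For complications, the stated comparison uses patients where the hypothesis concerns operations, and the operation counted is not named. On the likeliest reading the result carries no information about redo complications. On the least natural reading it would show a ratio of 1.90-1.97 with no true difference, given assumed rates of 3-10% and independent, equal risks.

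A reader might infer that the main result is undermined. It is not: reoperation as the primary outcome is unaffected, and the patient-level table suits the Aim for baseline and index-operation characteristics. This should be fixed, but it does not threaten the study.

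**What to change.** Add an operation-level analysis to part 1, with one row per anti-reflux operation.

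- Compare redo with all primary operations, including the primaries of patients reoperated later.
- Outcomes: length of stay, and complications within 30 days of that operation.
- Report estimates with 95% confidence intervals and patient-clustered standard errors, crude and adjusted for calendar year, age, sex and comorbidity.
- State how an operation is classed as primary or redo, using register data from 1996 as look-back.
- In the patient-level table, limit complications to the index operation and say so.
- Say what the mortality row means. If it means long-term death, treat reoperation as time-dependent, or replace the row with 30-day mortality per operation.

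**Cost.** SAP wording and some programming. Length of stay and deaths are already planned for retrieval. The Methods wording leaves it unclear whether 30-day diagnoses cover primary operations or only later procedures. If only the latter, the extract must be extended. According to the funding and ethics section, permissions are still to be obtained before the study starts, so this is best settled before data are requested.

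**Downside.** The conclusion may become that an increase cannot be excluded. With the assumed numbers and a 5% rate, the half-width of 4.4 to 2.5 percentage points is about half to nearly all of the rate itself (2.5 / 5 = 0.50; 4.4 / 5 = 0.88).

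### Mortality is tested between groups defined by later reoperation with tests that ignore person-time, so the comparison has built-in survival bias and cannot be interpreted

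*Combined protocol and SAP*

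**What the plan says.** The Methods section sets the cohort: "The population is defined as all adult Danish patients undergoing anti-reflux surgery", with operations from 2000 to 2017. Entry is therefore staggered and no fixed follow-up is given. On deaths it says: "From the Civic Register, data on mortality in the study period are retrieved". The 30-day window in the same section is attached to postoperative diagnoses, not to death.

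Part 1 of the statistical analysis opens with a list of descriptive items. The last is "mortality comparing patients with only primary anti-reflux surgery and patients with reoperation during the study period". The comparison "will be performed using Student's t-test, Chi2-test and Mann-Whitney-U test". The text does not say which test goes with which item; Chi2 is the natural one for the proportion dead.

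The only time-to-event model is described as follows: "Secondary analysis will be performed using Cox-regression investigating time to reoperation". Its outcome is reoperation, not death. The plan gives no time origin for mortality, no landmark, no time-varying reoperation status and no person-time analysis of death.

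**The concern.** Group membership is settled by an event after baseline that requires survival. A patient who dies two years after the primary operation without a redo can only be counted as primary-only. A patient reoperated in year six had to survive six years to be counted as reoperated. This is immortal-time bias, and it pulls the reoperated group's mortality down whatever redo surgery does.

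A second distortion usually runs the other way. Patients with longer observation have had more time to be reoperated and also more time to die. The reoperated group therefore has longer total follow-up, which raises its crude proportion dead. The listed tests deal with neither effect.

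This is the only mortality comparison in the plan. The Background cites a Danish study of 1997-2005 that found no significant mortality difference between redo and primary surgery. A null or favourable result here could be read as confirming it, although the comparison does not measure mortality related to redo.

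**Working it through.** The plan states no figure for this comparison, so there is none to reproduce. The check asks what the planned comparison would show if redo had no effect on death.

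**Inputs from the document (Background).** "An American study reported a cumulative five- and ten year incidence of reoperation of 5.2% and 6.9% respectively". The same section places the peak reoperation rate in year one.

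**Assumptions.** Reoperation is 2% at 1 year, and the 5-10 year slope continues to 18 years. The death hazard is 0.5%, 1% or 2% per year, either constant or rising 9% per year. Entry over 18 years is uniform, or falls or rises by 8% per year. Each scenario has 4 million simulated patients, grouped as the plan groups them.

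**Mechanism by hand.** Take a constant hazard h = 0.01 and 10 years of observation. From the primary operation, P(dead) = 1 - exp(-0.01 × 10) = 9.5%. For a patient reoperated at 2.5 years, about the simulated median, only the later 7.5 years can contain a death: 1 - exp(-0.01 × 7.5) = 7.2%. The ratio is 0.76 with no effect of redo.

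**One full scenario (uniform entry, constant 1% per year).**
- Dead: 6.83% of reoperated and 8.62% of primary-only patients. Risk ratio 0.79; odds ratio (0.0683/0.9317)/(0.0862/0.9138) = 0.78.
- Mean follow-up from the primary operation: 10.47 and 8.36 years.
- The reoperated group has 6.83 years after redo, so 10.47 - 6.83 = 3.64 years, or 35% of its follow-up, is guaranteed survival.
- Deaths per person-year from the primary operation: (0.0683/10.47)/(0.0862/8.36) = 0.63. Removing the follow-up imbalance alone exposes the bias more fully.

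**All entry patterns at a 1% starting hazard, no redo effect.**

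| Entry | Hazard | Dead, reoperated | Dead, primary only | Odds ratio |
|---|---|---|---|---|
| Uniform | constant | 6.83% | 8.62% | 0.78 |
| Uniform | rising | 13.91% | 14.75% | 0.93 |
| Falling | constant | 7.85% | 10.58% | 0.72 |
| Falling | rising | 16.74% | 19.14% | 0.85 |
| Rising | constant | 5.74% | 6.62% | 0.86 |
| Rising | rising | 10.75% | 10.65% | 1.01 |

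Over all three hazard levels the odds ratio runs from 0.71 to 1.02. A separate simulation on the same reoperation curve gave 0.67-0.86 with a constant hazard and 0.79-1.00 with a rising one. Together they support about 0.67 to 1.0. These are not hard limits: a steeper trend in entry widens the range at either end.

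**True excess after redo.** With a post-redo hazard ratio of 1.25, the crude odds ratio was 0.85-1.26 across scenarios. With 1.5 it was 1.17-1.45 (uniform entry), 1.03-1.25 (falling) and 1.28-1.50 (rising).

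**Check of the remedy.** When time before redo is counted as not reoperated, the null death-rate ratio returns to 0.98-1.01 under a constant hazard. Under a rising hazard the crude split gives 1.17-1.20, a false excess, because time after redo is later time. The model must therefore also control the time scale.

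**The case against.** The strongest defence is that the item is introduced as descriptive. Mortality is neither outcome nor covariate in the logistic or Cox models, and the aim concerns the course leading to reoperation and the use of treatment. That stands, and it limits the weight of the point. It does not remove it, because the plan applies formal tests.

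Several stronger readings are tempting, and the document does not support them:

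- *Redo will always look safer.* With rising entry and a rising death hazard the two distortions nearly cancel, and the document gives neither input. Cancellation by chance does not make the test valid, but the net direction is not certain.
- *The bias has one stable size.* An odds ratio near 0.8 whatever the death rate appears only if entry is uniform and the hazard constant. A constant hazard over 18 years is doubtful in ageing adults.
- *The bias is as large as under fixed follow-up.* At a fixed 10 years the null risk ratio is 0.66-0.75, but the plan does not restrict the comparison to patients with 10 years of observation.
- *A substantial excess would vanish.* A true hazard ratio of 1.5 stayed above 1 in every scenario, though attenuated in most and almost hidden with falling entry and a constant hazard.
- *The bias props up the study hypothesis.* The Background hypothesis names approach, length of stay, complications and dilatation, not mortality.

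The sponsor may have meant 30-day mortality after each operation. The text does not say so; if that was the intention, it should be written down.

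**Conclusion.** The flaw is real. Following the plan as written gives a mortality comparison that cannot be interpreted, because guaranteed survival before redo and unequal follow-up are mixed in proportions that the document does not fix. With no effect of redo the crude odds ratio would be about 0.67 to 1.0, and a true hazard ratio of 1.25 would appear as about 0.85 to 1.26, so a modest excess could be hidden or reversed.

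These figures rest on the cited American reoperation rates and on assumed values for the 1-year rate, entry pattern and death hazard. The structural fault does not depend on those values.

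A reader might infer that the main results are compromised. They are not affected by this point, since the primary logistic model has reoperation as its outcome. This should be fixed, but it is not critical to the study.

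**What to change.** 1. Remove mortality from the table grouped by eventual reoperation.
2. Report 30-day and 90-day mortality counted from each operation: from the primary operation for all patients, including those reoperated later, and from the redo for reoperated patients. Say how operations with less than 90 days of observation before the end of the data are handled.
3. If long-term mortality is wanted, specify a Cox model for death with reoperation as a time-dependent exposure, each patient counting as not reoperated until the redo date. State the time scale: time since primary surgery with adjustment for age, or attained age.

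The cost is SAP wording and little programming. The planned time-to-reoperation model already needs operation dates, and mortality data are already retrieved; the plan should confirm that these include the date of death. The drawback is that 30-day and 90-day deaths will be few, particularly after redo, so the intervals will be wide and should be reported as such.

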## Background

Episodic reflux of gastric contents to the esophagus is physiological but is considered gastroesophageal reflux disease (GERD) when accompanied by bothersome symptoms, typically heartburn, regurgitation or retrosternal pain. Extra-esophageal symptoms such as asthma, laryngitis and chronic cough may also occur (1). GERD is a complex and multifaceted disease (2, 3), affecting 10-20% of the Western population (4) and has been shown to significantly reduce the quality of life (5). Worldwide, the prevalence of GERD has been increasing (6-8). Treatment of GERD consists of anti-secretory drugs, mainly proton pump inhibitors (PPI), or anti-reflux surgery. Laparoscopic anti-reflux surgery is considered standard of care in surgical treatment of gastro-esophageal reflux disease (9) and with careful patient selection based on thorough preoperative workup (10), symptom control and patient satisfaction are high compared to medical therapy. This has previously been demonstrated in meta-analysis (11, 12).

From 1990-2000 the utilization of anti-reflux surgery in the USA rose to 16.7 procedures per 100.000 inhabitants with a concomitant rise in the use of the transabdominal laparoscopic approach. This resulted in a decline of perioperative mortality and morbidity (13, 14). The rate of anti-reflux surgery dropped to 6.1 procedures per 100.000 inhabitants in 2010, men the patients were now older with significantly higher levels of comorbidity. Despite this, length of stay, morbidity and mortality was reduced even further. The laparoscopic approach is used in 80% of American procedures and the rate has not changed during the last ten years. It is unknown whether Denmark follows the same trends, as the popularity of anti-reflux surgery has been somewhat limited and the surgical setup is different with significantly fewer centers.

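### The hypothesis of no extra complications or stay after redo surgery has no adjusted analysis: the operation counted is undefined and calendar year is uncontrolled

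*Combined protocol and SAP*

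**What the plan says.** The last paragraph of the Background holds two relevant hypotheses. The first is that redo surgery in 2000-2017 brought no increase in stay or complications over primary surgery. The second is that "Due to increased surgical experience the rate of complications is decreasing despite increased comorbidity".

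In Statistical analysis, part 1, the groups are formed by "comparing patients with only primary anti-reflux surgery and patients with reoperation during the study period". The outcomes in that comparison include "complications to surgery, rate of endoscopic dilation and mortality", and it "will be performed using Student's t-test, Chi2-test and Mann-Whitney-U test". Length of stay is retrieved (Methods) but is not in this list or in any other analysis.

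The two patient-level models have a different outcome: "Logistic regression will be performed with reoperation (laparoscopic, open or other) as primary outcome" and "Secondary analysis will be performed using Cox-regression investigating time to reoperation". Complications enter both as an independent variable, and calendar year is in neither list. The only model over calendar time is in part 2, and it concerns the number of operations: "Trends in the utilization of surgery are investigated with trend-analysis in the form of Poisson-regression".

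**The concern.** A redo can only follow its own primary, so redo operations tend to fall later in the study window. If complications are falling, later operations have fewer of them whatever their type. A crude comparison then mixes the effect of operation type with the effect of calendar year, and the plan has no model that separates them.

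The plan also leaves open which operation's complications are counted for a reoperated patient. That choice changes the sign of the bias. At the redo, the operations compared are later than the primary-only ones. At the primary, they are earlier, because a patient operated on early in the window has had longer to be reoperated.

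At stake is a published conclusion on whether redo surgery is as safe as primary surgery. The falling-complications hypothesis is affected too, since no listed analysis addresses it.

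**Working it through.** The plan states no complication rate, trend size, sample size or power, so there is no design figure to reproduce. The check asks what crude ratio would appear if redo and primary surgery had equal risk within each calendar year.

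**Inputs from the documents**
- Window: 18 years, 2000-2017; register data from 1996 (Methods).
- Cumulative reoperation of 5.2% at 5 years and 6.9% at 10 years, with the highest rate in the first year (Background, American study).
- US volume falling from 16.7 to 6.1 per 100,000 by 2010 (Background). Taken over 10 years, ln(6.1/16.7)/10 = -0.101 a year. This is one scenario only, because the Background says it is unknown whether Denmark follows the US trend.

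**Assumptions**
- Reoperation of 2% or 3% at 1 year; half the 5-10 year slope after year 10; linear between points.
- Complications fall 2%, 5% or 10% a year.
- Surgical volume changes by about -10%, -5%, 0 or +5% a year.
- Redos of 1996-1999 primaries are excluded or included.

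**Formula.** Let v(s) be primary volume at calendar time s, F(t) the cumulative reoperation curve with density f(t), and d the yearly fall. The calendar densities are:
- primary-only operations: v(s)[1 - F(18 - s)]
- primaries of reoperated patients: v(s)F(18 - s)
- redo operations at time c: the integral of v(s)f(c - s) over s

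The null ratio is the mean of (1 - d)^time in the reoperated group divided by the same mean in the primary-only group.

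**Calendar position, flat volume, no earlier primaries** (years from the start of 2000): primary-only 9.1; redo operations 10.5-10.7, so 1.4-1.6 years later; primaries of reoperated patients 7.3-7.5, so about 1.6-1.8 years earlier.

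**Null ratio in that setting**

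| Yearly fall | Counted at redo | Counted at primary |
|---|---|---|
| 2% | 0.968-0.972 | 1.031-1.035 |
| 5% | 0.916-0.927 | 1.077-1.087 |
| 10% | 0.827-0.849 | 1.147-1.165 |

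Hand check at 5%: 0.95^1.57 = 0.92 and 0.95^1.38 = 0.93 at the redo; 0.95^-1.78 = 1.10 and 0.95^-1.57 = 1.08 at the primary. These agree closely with the table.

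**Over all scenarios.** Redo operations are later in every one, by about 0.4-2.7 years, and the null ratio is 0.76-0.99. The gap is smallest when volume rises and redos of 1996-1999 primaries are included. It is largest under the US-like volume decline. Counted at the primary, index operations are 1.0-2.0 years earlier and the null ratio is 1.02-1.20.

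**What an excess would look like, counted at the redo** (flat volume, 3% at 1 year). With a 5% yearly fall, a true ratio of 1.3 appears as 1.3 x 0.927 = 1.21, and 1.5 as 1.39. With a 10% fall, 1.2 appears as 1.2 x 0.849 = 1.02, and 1.5 as 1.27.

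**The case against.** **The comparison is labelled descriptive.** That is so, but it applies significance tests and is the only listed analysis bearing on a stated hypothesis. If it is purely descriptive, the hypothesis has no inferential analysis at all.

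**The plan hides a redo excess.** A reader might infer this, but the documents do not support it as a one-directional claim. It requires complications to be counted at the redo. The groups are patients, not operations, and both regressions use complications as a predictor of reoperation, which fits the primary operation more naturally. On that reading the bias runs against the hypothesis. What stands is that the direction cannot be known until the term is defined.

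**Stay is expected to shorten over time.** A reader might infer this from "length of stay, morbidity and mortality was reduced even further", but that sentence describes US history, and the hypothesis paragraph predicts a trend only for complications. No bias can be sized for an analysis of stay that the plan does not list. The gap for stay is the missing analysis.

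**The distortion is small beside sampling error.** This largely stands. Take 4000 patients, 5% reoperated and 5% complications, all assumed. There are then 200 x 0.05 = 10 redo events and 3800 x 0.05 = 190 others. The standard error of the log ratio is sqrt(1/10 - 1/200 + 1/190 - 1/3800) = 0.32, giving 95% limits around 1 of about 0.54-1.86. A 7-8% shift is well inside that. It is nevertheless systematic, and where the claim is no increase, attenuation favours the claim.

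**Conclusion.** The point holds as a gap in the analysis with a confounded contrast. From the text alone, the redo-versus-primary hypothesis rests on unadjusted tests, the operation to which complications belong is not stated, stay has no listed analysis, and no patient-level model contains calendar year.

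That the crude contrast is confounded follows if complications fall as the Background hypothesises. The size does not follow from the documents, which give neither an annual decline nor a Danish calendar distribution. Under the stated assumptions the effect is modest: about 7-8% attenuation with a 5% yearly fall and flat volume, when complications are counted at the redo. Over all scenarios it runs from 1% to 24%, and the upper end needs both a 10% yearly fall and a US-like decline in volume. Counted at the primary, it is an inflation of 2-20%. A large redo excess would be reduced, not erased. Rising comorbidity, which the Background also expects, could offset part of the trend; that too calls for adjustment.

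**What to change.** 1. State that complications and length of stay are attributed to each operation, primary or redo, and whether redos of primaries done before 2000 are included.
2. Test the redo-versus-primary hypothesis by regression with the operation as unit: logistic for 30-day complication, and log-linear or negative binomial for length of stay. Use operation type as the exposure. Adjust for year of that operation, age, sex, Charlson index, ASA score and priority. Use patient-clustered standard errors, because one patient can contribute both a primary and a redo.
3. Report the year term of the complication model as the case-mix-adjusted analysis of the falling-complications hypothesis.
4. Keep the two-group tests as description, and give the adjusted ratios with confidence intervals.

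The cost is two additional models and a paragraph of plan wording. The clinical covariates are already retrieved under Methods, and operation year follows from the date of surgery. The downside is limited precision: with few redo events the intervals will be wide, and a non-significant result should not be read as showing no increase.
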